[figure not shown]
[figure not shown]

Title: Predicting Pain Response to Transcranial Direct Current Stimulation for Phantom Limb Pain in Limb Amputees.

Protocol: 2015P002525

Date: 06/06/2017

[figure not shown]
II. SPECIFIC AIMS

The specific aims of this experiment are as follows:

Aim 1: To assess the predictors of response to transcranial direct current stimulation (tDCS) in phantom limb pain of subjects with limb amputation. We will explore the aim 1 in an open-label pilot study in which patients will receive active tDCS during 5 daily sessions.

The primary endpoint will evaluate the predictors of pain response to tDCS measured by changes in PLP as indexed by a Visual Analog Scale. The study will require a total of 4 weeks to be completed. The first week, each patient will give daily reports of their pain using a VAS,

accounting for their PLP experience in the past 24hs. This initial baseline week will be followed by five days of treatment and a final 2-week follow-up period without any treatment to examine the lasting effects of the therapy. We will examine whether the following predictors are associated with treatment response: lower or upper limb, bilateral or unilateral and traumatic or non-traumatic amputation, baseline pain, age and gender by building a multivariate model.

IV. SUBJECT SELECTION

In this pilot study, we will recruit 50 subjects with phantom limb pain (PLP) of any etiology (traumatic, vascular disease, diabetic amputees or others). Subjects will need to meet all of the following inclusion criteria and none of the following exclusion criteria:

Inclusion Criteria:

1. Able to provide informed consent to participate in the study.
2. Subject is older than 18 years.
3. 3 months of phantom limb pain (experienced regularly for at least once a week) after the amputated limb has completely healed.*
4. Average pain of at least 4 on a numeric rating scale in the previous week (NRS; ranging from 0 to 10).
5. If the subject is taking any medications, dosages must be stable for at least 2 weeks prior to the enrollment of the study.

*The healing status of the limb will need to be confirmed by the subject's physician or by the physician of the protocol [name] (Co-Investigator).

Exclusion Criteria:

[figure not shown]
1. Pregnancy or trying to become pregnant in the next 2 months.
2. History of alcohol or drug abuse within the past 6 months as self-reported.
3. Presence of the following contraindication to transcranial direct current stimulation

✓ Ferromagnetic metal in the head (e.g., plates or pins, bullets, shrapnel)

✓ Implanted head electronic medical devices (e.g., cochlear implants)

4. Head injury resulting in loss of consciousness for at least 30 min or post-traumatic amnesia for greater than 24 hours, as self-reported

5. Unstable medical conditions (e.g. uncontrolled diabetes, uncompensated cardiac issues, heart failure or chronic obstructive pulmonary disease).
6. Uncontrolled epilepsy, as defined by previous clinical seizure in the past 3 months in patients with treatment for epilepsy.
7. Suffering from severe depression (as defined by a score of >30 in the Beck Depression Inventory).*
8. History of unexplained fainting spells or loss of consciousness as self-reported during the last 2 years.
9. History of neurosurgery, as self-reported.

Description of interventions

tDCS Stimulation Protocol:

We will use Soterix Medical 1×1 tDCS stimulators device (© Soterix Medical Inc.), its sends a low-level current from the positive electrode, anode, to the negative electrode, cathode. During tDCS, low amplitude direct currents are applied via scalp electrodes and penetrate the skull to enter the brain. Direct current will be transferred by a saline-soaked pair of surface sponge electrodes (35 cm²) and delivered by a specially developed, battery-driven, constant current

stimulator with a maximum output of 10 mA. Subjects will receive daily stimulation sessions with active anodal tDCS for 5 days. Subjects are allowed to reschedule up to 1 stimulation visit. During each session, an anodal electrode will be placed over the primary motor cortex (M1), contralateral to the most painful amputation side and the cathode over the contralateral supraorbital area. Two milliamps of tDCS will be applied for 20 minutes [14].

DESCRIPTION OF ASSESSMENTS:

The following tests will be administered:

Visual Analogue Scale (VAS) for Pain: The VAS is a common assessment used which asks subjects to self-reportedly measure their pain on a visual scale (i.e., unbearable to none). We will use a VAS to determine subjects' pain scores. Subjects will rate their pain from 0 – indicating no pain at all, to 10 – indicating the worst pain felt. This scale is also colored, from green (at 0) to red (at 10), as a visual indicator of pain. This assessment tool is frequently used in many research studies evaluating pain levels [15, 19, 20].

Visual Analogue Scale (VAS) for Stump Pain: any painful sensation in the stump. Subjects will rate their stump pain from 0 – indicating no pain at all, to 10 – indicating the worst pain felt. The scale will include colors to help in identifying the correct response [15].

Visual Analog Scale (VAS) for Phantom Limb Sensation: all non-painful sensations in the amputated part of the limb. Subjects will be presented with a scale starting at 0- No phantom limb sensation, to 10 – Full sensation of the amputated limb. The scale will include colors to help in identifying the correct response [15].

Visual Analog Scale (VAS) for Phantom Limb telescoping: refers to the shrinking and retraction of the phantom towards the residual limb. Subjects will be presented with a scale starting at 0 - indicated that the phantom was enlarged, and 10 meant that the phantom was completely retracted into the stump the scale will include colors to help in identifying the correct response [15].

Adapted Groningen Questionnaire after Arm Amputation: This questionnaire will be applied to obtain information's concerning complaints that may be developed after arm amputation and has been used in several clinical trials assessing PLP [21].

Adapted Groningen Questionnaire after Leg Amputation: This questionnaire is originally meant to obtain information's concerning complaints that may be developed after arm amputation. We adapted the current arm version for lower limb amputation. This questionnaire [21] has been used in several clinical trials assessing PLP.

Pain and medication diary: To help monitor pain levels and medication use information, as well as safety. Subjects will be asked to record the number of phantom limb episodes on a daily basis, using a pain diary. They will record the intensity of the strongest episode as well as phantom limb sensation and stump pain on a colored visual analog scale included in the diary, where 0 represents no pain at all and 10 represents the highest pain the patient has ever felt. Moreover subjects will record their current medications and dosages daily in a pain medication diary, until completion of the study.

Beck depression Inventory: This self-report inventory consists of 21 multiple-choice questions and is widely used method to classify depression severity. It assesses for the presence of several symptoms related to depression, such as irritability, hopelessness and decreased cognitive performance. Physical symptoms such as weight loss and fatigue are also included. This instrument has been used previously to evaluate depression severity in patients with phantom limb pain [22], as well as in other chronic pain conditions [23, 24].

Beck anxiety Inventory: This self-report inventory consists of 21 multiple-choice questions about how the subject has been feeling in the last week, expressed as common symptoms of anxiety (such as numbness and tingling, sweating not due to heat, and fear of the worst happening). It is designed for an age range of 17–80 years old. Each question has the same set of four possible answer choices, which are arranged in columns and are answered by marking the appropriate one with a cross [25].

Mini Mental State examination (MMSE): This is a sensitive, valid and reliable 30-point questionnaire that is used extensively in clinical and research settings to measure cognitive impairment. This instrument will be used as a brief screening of cognitive abilities. It will be used as a baseline evaluation [26].

Quality of Life Assessment (Short version of SF-36): The short version of the SF-36 health survey is used as a measurement of quality of life. It provides a profile of functional health and well-being scores. It is also used as a psychometrical index of physical and mental health. This instrument is widely used as a quality of life assessment in patients after an amputation and those suffering from phantom limb pain [27-30].

Stroop test: In this task the subject is presented with names of colors written in the same color or in a different color, thus on the one hand the word names a color (red) and is written in another color (blue). In this task, the automatized behavior (reading) is in conflict with the desired response (naming the color). The Subject has to inhibit/suppress the automatic response of reading and naming the color the word is written in. The Stroop is one of the most commonly used tools for determining attentional problems, also used to assess executive function and working memory [31, 32]. Stroop test will be applied as a preliminary safety assessment of cognitive changes from baseline to post and follow-up visits.

Side Effects Questionnaire for tDCS: At each stimulation session, subjects will complete a questionnaire to evaluate potential adverse effects of tDCS (tingling, burning sensation, headache, neck pain, mood alterations) on a 4-point scale (None, mild, moderate and severe). The subjects will be asked whether they have experienced any side effects in an open-ended manner and they will then be specifically asked about headache, neck pain, scalp pain, scalp burns, tingling, skin redness, sleepiness, trouble concentrating, and acute mood change. If any side effects are reported, the degree of relatedness to the intervention will be assessed on a 5-point scale. This type of adverse events questionnaire has been used frequently in our previous tDCS studies [23], including in patients with phantom limb pain [33].

VI. BIOSTATISTICAL ANALYSIS

Data forms and questionnaires will be coded in a standardized manner, and double-entered into our database. Digital measures/recordings will be similarly tracked in our database and regularly backed up. Analyses will be conducted using standard statistical software such as SAS and Matlab.

Sample size calculation:

This is an open label pilot study, we aim to recruit 50 participants with upper or lower, bilateral or unilateral amputation of any etiology that present chronic phantom limb pain at least in one of the amputated limbs. Given we are planning to build a multivariate regression analysis with up to 5 variables and considering 10 subjects per variable, a sample of 50 subjects would be appropriate for this exploratory analysis. The goal of this study is to provide data to generate further hypothesis regarding whether demographic and clinical factors influence treatment response as to be used for designing a randomized clinical trial (RCT). Therefore the goal of this study is not confirm a priori hypothesis but to provide critical data to design a RCT testing the effects of tDCS in this population of PLP.

Statistical Analysis

For aim 1: The primary outcome is PLP indexed by VAS. PLP will be analyzed using changes in pain. To analyze these data, we will build a multivariate linear regression model in which the dependent variable will be the Visual Analogue Scale (VAS) for PLP using the following covariates: baseline pain (VAS), amputated limb (upper/lower), etiology of amputation (traumatic/ non traumatic), laterality of amputation (unilateral/bilateral), age, and gender. The first step will be perform a univariate analysis for each one of our predictors using univariate linear regression and obtain the values for the unadjusted b coefficients and 95% confidence intervals (CIs). After that, predictors associated with the outcome at a p level <0.01 will be used to build a multivariate linear regression using a forward stepwise model.

Additional statistical models for secondary outcomes will be developed in an exploratory manner. Therefore, we will not correct P values for multiple comparisons.

References

1. Flor, H., Phantom-limb pain: characteristics, causes, and treatment. *Lancet Neurol*, 2002. 1(3): p. 182-9.
2. Nikolajsen, L. and T. Staehelin Jensen, Phantom limb pain. *Curr Rev Pain*, 2000. 4(2): p. 166-70.
3. Manchikanti, L. and V. Singh, Managing phantom pain. *Pain Physician*, 2004. 7(3): p. 365-75.
4. Birbaumer, N., et al., Effects of regional anesthesia on phantom limb pain are mirrored in changes in cortical reorganization. *J Neurosci*, 1997. 17(14): p. 5503-8.
5. Borsook, D., et al., Acute plasticity in the human somatosensory cortex following amputation. *Neuroreport*, 1998. 9(6): p. 1013-7.
6. Flor, H., et al., Phantom-limb pain as a perceptual correlate of cortical reorganization following arm amputation. *Nature*, 1995. 375(6531): p. 482-4.
7. Grusser, S.M., et al., The relationship of perceptual phenomena and cortical reorganization in upper extremity amputees. *Neuroscience*, 2001. 102(2): p. 263-72.

8. Montoya, P., et al., The cortical somatotopic map and phantom phenomena in subjects with congenital limb atrophy and traumatic amputees with phantom limb pain. *Eur J Neurosci*, 1998. 10(3): p. 1095-102.
9. Ramachandran, V.S., D. Rogers-Ramachandran, and M. Stewart, Perceptual correlates of massive cortical reorganization. *Science*, 1992. 258(5085): p. 1159-60.
10. Davis, K.D., et al., Event-related fMRI of pain: entering a new era in imaging pain. *Neuroreport*, 1998. 9(13): p. 3019-23.

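### Baseline pain is screened as a predictor of change from that same baseline in a single active arm, so it can pass p<0.01 more often than 1% of the time when no patient truly responds differently

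*Combined protocol and SAP*

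**What the plan says.** Specific Aims (section II) sets the endpoint as "predictors of pain response to tDCS measured by changes in PLP as indexed by a Visual Analog Scale". All patients receive open-label active tDCS, so there is no control arm. The predictors of treatment response named there include "traumatic or non-traumatic amputation, baseline pain, age and gender by building a multivariate model".

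Statistical Analysis (section VI) says "PLP will be analyzed using changes in pain". It then names the dependent variable simply as the VAS for PLP and lists six covariates, baseline VAS among them. Each is tested by univariate linear regression, and those with p<0.01 go forward to a forward stepwise model. Nothing exempts baseline pain from the screen, and the link between baseline and change is not mentioned.

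Three other provisions affect the size of the problem:
- **Baseline ratings.** "The first week, each patient will give daily reports of their pain using a VAS" (Specific Aims). The visible text does not say whether the week is averaged.
- **Diary.** "They will record the intensity of the strongest episode as well as phantom limb sensation and stump pain" (Description of Assessments). This is a peak score, not an average.
- **Entry floor.** "Average pain of at least 4 on a numeric rating scale in the previous week" (Inclusion Criteria).

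The purpose is stated under Sample size calculation: "The goal of this study is to provide data to generate further hypothesis regarding whether demographic and clinical factors influence treatment response", for use in designing a randomised trial.

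**The concern.** A patient whose baseline happens to be recorded too high will, on average, show a fall afterwards whatever the treatment does. When change is regressed on that same baseline, the error enters the predictor with a plus sign and the outcome with a minus sign. The null slope is therefore negative rather than zero, and the 1% threshold does not hold for this candidate. A control arm would show the same artefact and allow it to be subtracted, but this design has none.

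The bias runs one way, towards the plausible message that patients in more pain respond better to tDCS. The output is meant to shape a randomised trial, so the artefact could be passed on as a finding about who benefits, for instance as an enrichment or stratification factor.

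**Working it through.** **The plan's own figure.** Sample size calculation: 10 subjects × 5 variables = 50, which reproduces. Six candidates at 10 each would be 60, but the statement refers to "multivariate regression analysis with up to 5 variables and considering 10 subjects per variable" and the screen may leave five or fewer, so this is not a contradiction.

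**Null slope.** Let baseline be b = T + e1 and post score f = T − Δ + e2, with Δ the same for everyone and independent errors. Change is f − b = −Δ + e2 − e1. Then

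slope = cov(b, f − b)/var(b) = −var(e1)/[var(T) + var(e1)] = −(1 − R),

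where R is the reliability of the baseline summary. Correlated baseline and post errors make it smaller in size.

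**Reliability of a 7-day mean.** With single-day reliability ρ and day-to-day autocorrelation φ (both assumed), R = ρ/[ρ + (1 − ρ)v], where v = [7 + 2Σ(7 − k)φ^k]/49, summed over k = 1 to 6.
- ρ = 0.8, φ = 0: v = 1/7 = 0.143; 1 − R = 0.0286/0.8286 = 0.03.
- ρ = 0.5, φ = 0.5: v = 17.03/49 = 0.348; 1 − R = 0.174/0.674 = 0.26.

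The artefact is thus 0.03 to 0.26 points of apparent extra response per baseline point.

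**Selection threshold.** For n = 50 and two-sided p<0.01 (sidedness assumed), the critical |r| is 0.361. For single readings with equal variances, the correlation of baseline with change is −√[(1 − c)/2], where c is the baseline-to-post correlation. This is −0.50 at c = 0.5 and −0.32 at c = 0.8. Simulated selection is 89% and 38%; an unrelated predictor such as age is selected about 1% of the time.

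**Simulated false selection of baseline.** Stable patient level plus AR(1) noise, total SD 2, ρ = 0.5/0.7/0.8, φ = 0/0.3/0.5, identical true response. Runs with a floor clip the VAS to 0–10 with mean 5 or 6.

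| Baseline / post score | No floor | Floor on a separate earlier week | Floor on baseline-week mean |
|---|---|---|---|
| 7-day mean / one day | 1.0–20.6% | 1.5–28.5% | 0.8–12.1% |
| 7-day mean / 5 treatment days | 3.9–33.6% | not run | not run |
| 7-day mean / 7-day mean | 4.8–49.8% | not run | not run |
| Single day / single day | 34.6–90.7% | not run | not run |
| Days 1–3 as predictor, change from days 5–7 | 0.5–2.1% | 0.6–2.2% | 0.6–3.5% (4.2% in a smaller run) |

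The first row is mild because noise in a one-day post score widens the residual without adding to the slope.

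**Post-treatment VAS as dependent variable.** Baseline is selected in about 88–100% without a floor. With the floor it is 86–100% for a 7-day baseline and 47–100% for single days. The cause is persistence of pain within patients.

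**The other five predictors.** Assume a 25/25 grouping factor with no effect of its own, a 2-point group difference in true baseline pain, and 7-day means on both sides. False selection of the factor at p<0.01:

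| True slope of response on baseline | Unadjusted change | Baseline-adjusted |
|---|---|---|
| 0 | about 1% | 1.5–12% |
| 0.3 | 10–19% | 1–3% |
| 0.5 | 29–42% | 1–3% |

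Neither analysis is safe in general, and the data cannot be assumed to favour either.

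**The case against.** **The natural reading gives a small effect.** A baseline week is defined, and averaging it removes most of the noise. With independent daily errors, a 7-day mean and a one-day post score, false selection is 4.1%, 2.3% and 1.4% at reliability 0.5, 0.7 and 0.9. With the floor on the baseline-week mean the range starts at about 1%, so it includes no inflation. If true response varies between patients independently of baseline, the rate also drops: for single readings at reliability 0.7 it goes from 60% to 18% when the response SD equals the pain SD, although the biased slope remains. All of this stands for size. It does not restore a zero null slope.

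**The study is exploratory.** True, and it limits the weight. But waiving multiplicity correction does not cover a candidate whose own 1% level fails in a known direction.

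**Baseline is an ordinary covariate.** As adjustment, yes. A reader might infer that baseline should leave the model altogether and that unadjusted change should be the only analysis. The second table shows why not: if response does depend on baseline, dropping the adjustment can mislead about the other predictors far more than keeping it.

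**The 88–100% figure.** A reader might take this as a false-positive rate. It is not. Pain tracks over time, and including baseline in a model for post-treatment VAS is legitimate. It misleads only if reported as differential response.

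**The public text may be incomplete.** Section numbers run II, IV, VI, so unstated summaries are treated here as unknown, not as omissions.

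**Conclusion.** The concern holds in direction and is uncertain in size. As written, the screen can select baseline pain as a predictor of response when no patient differs in true response, and the error always favours higher baselines. Under the assumed reliability and autocorrelation, false selection against a nominal 1% is:
- about 1–29% for a 7-day-mean baseline with a one-day post score, across floor placements (about 1–12% if the floor acts on the baseline-week mean, and close to nil with a precise baseline);
- up to about 50% for 7-day means on both sides, without a floor;
- 35–90% for single-day scores, without a floor.

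It concerns one of six predictors in a hypothesis-generating pilot, so it is minor to moderate, but worth correcting before analysis because predicting response is the study's only stated aim. The documents do not support a wider conclusion that the screens of the other five predictors are invalid, or that a baseline association, if found, must be artefact. This regression simply cannot tell artefact from true dependence.

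**What to change.** 1. Take baseline pain out of the p<0.01 screen as a predictor of response, and do not interpret its coefficient in this regression as dependence of response on baseline.
2. State that the dependent variable is change in PLP VAS, with the baseline and post-treatment summaries if these are not fixed elsewhere. Describe it as change during open-label treatment.
3. If dependence on baseline is of interest, estimate it with separate days on each side: for example, the mean of days 1–3 as predictor and change measured from the mean of days 5–7. The planned daily ratings suffice. False selection is then about 0.5–2%, or up to about 4% if the floor acts on the baseline-week mean.
4. Keep baseline available as an adjustment covariate. For the other five predictors, report unadjusted and baseline-adjusted change estimates side by side, and call a predictor robust only if the two agree.

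**Cost.** SAP wording, a few lines of code and somewhat more reporting; no new data. The split week is less precise: a 3-day mean has 1.8–2.3 times the error variance of a 7-day mean. For an assumed true slope of 0.5 (other response SD 1) and a 7-day post mean, power is about 48–60%, 84–92% and 95–98% at reliability 0.5, 0.7 and 0.8. With a one-day post score it is about 28–33%, 68–73% and 88–90%.

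### Exclusion 6 bars a recent seizure only in people treated for epilepsy, so some untreated people with a recognised seizure are not clearly excluded

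*Combined protocol and SAP*

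**What the plan says.** Section IV (Subject Selection) sets the eligibility rule: "Subjects will need to meet all of the following inclusion criteria and none of the following exclusion criteria". Nine exclusions are listed. Those that bear on seizures are:

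- Exclusion 6: "Uncontrolled epilepsy, as defined by previous clinical seizure in the past 3 months in patients with treatment for epilepsy".
- Exclusion 8: "History of unexplained fainting spells or loss of consciousness as self-reported during the last 2 years".
- Exclusion 5, an open list: "Unstable medical conditions (e.g. uncontrolled diabetes, uncompensated cardiac issues, heart failure or chronic obstructive pulmonary disease").
- Exclusion 4: "Head injury resulting in loss of consciousness for at least 30 min or post-traumatic amnesia for greater than 24 hours, as self-reported".

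Inclusion 5 adds a condition on drug treatment: "If the subject is taking any medications, dosages must be stable for at least 2 weeks prior to the enrollment of the study".

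On exposure, Aim 1 in Section II says that "patients will receive active tDCS during 5 daily sessions" in an open-label pilot. The tDCS Stimulation Protocol gives the dose: "Two milliamps of tDCS will be applied for 20 minutes".

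**The concern.** The label of exclusion 6 is uncontrolled epilepsy, but the definition attached to it is narrower than the label. It requires a recent seizure and also current treatment. A person with known, active, untreated epilepsy fits the label and fails the definition.

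The result runs the wrong way. By writing this exclusion the sponsor decided that a seizure in the last 3 months is a reason not to stimulate a treated patient. The wording then leaves a person with the same seizure and no treatment outside the rule, and the plan gives no reason for being more permissive with that person.

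What is at stake is participant safety, not inference. There is no sham arm, so anyone who is enrolled through the gap receives active stimulation on 5 days. The primary endpoint, the sample size of 50 and the regression analysis do not depend on this criterion.

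**Working it through.** The plan states no figure on this point, so the check is one of coverage. Passing exclusion 6 does not admit anyone by itself, because a subject must clear every exclusion. Each criterion was therefore set against one case: an untreated person with a recognised clinical seizure in the past 3 months.

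**Criterion by criterion**

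- Exclusion 6: not met, because the person is not treated for epilepsy.
- Exclusion 8: met if consciousness was lost without explanation. Not met if consciousness was kept. If it was lost and the cause is known, the answer depends on grammar. If *unexplained* governs both fainting and loss of consciousness (strict reading), the criterion is not met. If it governs fainting alone (broad reading), it is met.
- Exclusion 5: does not name seizures. Its examples are metabolic, cardiac and pulmonary. It can be applied by judgement.
- Exclusions 2, 4 and 9: reach some people through a cause (alcohol or drug abuse in the past 6 months, serious head injury, neurosurgery), not through the seizure.
- Exclusion 3: lists only metal in the head and implanted head devices.
- Exclusions 1 and 7: pregnancy and severe depression, not relevant here.
- Inclusion 5: concerns drugs the person is taking, so it does not reach someone who never started epilepsy treatment. The other inclusion criteria do not mention seizures.

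**Count of profiles**

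Take a recognised seizure in the past 3 months as given. Cross treatment (2 levels) with consciousness (3 levels): 2 × 3 = 6 profiles. Apply exclusions 6 and 8 only.

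| Treated for epilepsy | Consciousness | No. 6 | No. 8, strict | No. 8, broad | Covered by 6 or 8? |
|---|---|---|---|---|---|
| Yes | Kept | Yes | No | No | Yes |
| Yes | Lost, unexplained | Yes | Yes | Yes | Yes |
| Yes | Lost, explained | Yes | No | Yes | Yes |
| No | Kept | No | No | No | **No** |
| No | Lost, unexplained | No | Yes | Yes | Yes |
| No | Lost, explained | No | No | Yes | **Strict: no.** Broad: yes |

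Strict reading: 6 − 3 (treated) − 1 (untreated, unexplained loss) = 2 uncovered. Broad reading: 6 − 3 − 2 = 1 uncovered. Every uncovered profile is untreated.

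If exclusion 6 no longer depends on treatment, it covers all six profiles and none is left. That follows directly from the wording and is not an empirical result.

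**The case against.** The strongest reply is that exclusion 5 already provides a route. It is an open list, and a recognised untreated seizure within 3 months fits the ordinary meaning of an unstable condition. Its own examples need clinical judgement too. This stands in part: a careful investigator could exclude the person. But exclusion 6 deals with seizures specifically, and a screener could reasonably take it as the governing rule and see that it is not met. The more general criterion is then a discretionary backstop.

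A second reply is that the documents do not show that this stimulation is hazardous after a seizure. Seizure is not among the contraindications in exclusion 3, and exclusion 6 admits treated epilepsy with no seizure in the past 3 months. It is right that no size of risk can be given. The point does not need one: the sponsor's own criterion treats a recent seizure as a reason not to stimulate.

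Third, the available text may be incomplete on safety. The section numbers run II, IV, VI, and several references on stimulation safety are not cited in what can be read. Risk or screening text elsewhere could narrow the gap in practice. The numbered exclusions 1 to 9 appear intact, however, so the wording problem in no. 6 remains.

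Fourth, the profile count gives the profiles no weights and leaves out exclusion 5 and the exclusions by cause. That is correct. It shows where the gap lies, not how many people fall into it.

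Finally, it can be said that excluding any clinical seizure goes beyond the label of uncontrolled epilepsy, and that deleting the treatment qualifier would be enough. Deleting it would leave a seizure in the past 3 months as the whole definition, which excludes essentially the same people, including those with a single provoked seizure. The two changes differ in naming more than in effect.

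**Conclusion.** The concern holds. As written, exclusion 6 does not cover an untreated person with a recognised seizure in the past 3 months, and no other listed criterion clearly covers that person when consciousness was kept. When consciousness was lost for a known reason, coverage depends on how exclusion 8 is read.

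The gap is narrow: two of six profiles on the strict reading, one of six on the broad reading. The documents give no seizure frequency, so the number affected among 50 subjects cannot be estimated and may be zero. The conclusion rests on reading the stated definition as the operative test, and on exclusion 5 being a matter of judgement for this case. It is a cheap improvement to a participant-safety rule that the sponsor should make.

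**What to change.** Reword exclusion 6 so that it does not depend on treatment status, for example: *uncontrolled epilepsy, or any clinical seizure within the last 3 months, whether or not the person is being treated for epilepsy*. Naming the seizure separately avoids calling a single provoked seizure epilepsy. Keep the 3-month window and leave exclusion 8 as it is.

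The cost is a one-line amendment and an edit to the screening form. A few more candidates might be excluded, including some with a single provoked seizure. The documents do not allow that number to be estimated, and candidates with alcohol or drug abuse in the past 6 months are already out under exclusion 2.

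### The diary paragraph puts non-painful phantom limb sensation on a pain-anchored scale, so a diary sensation score given on those anchors would not measure what the protocol defines (minor)

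*Combined protocol and SAP*

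**What the plan says.** All the relevant text is in the combined protocol and SAP, under Description of Assessments.

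- **VAS for Phantom Limb Sensation.** The construct is defined as "all non-painful sensations in the amputated part of the limb", and the scale runs from "0- No phantom limb sensation, to 10 – Full sensation of the amputated limb".
- **VAS for Stump Pain.** "Subjects will rate their stump pain from 0 – indicating no pain at all, to 10 – indicating the worst pain felt".
- **Pain and medication diary.** The stated purpose is "To help monitor pain levels and medication use information, as well as safety". On content: "They will record the intensity of the strongest episode as well as phantom limb sensation and stump pain on a colored visual analog scale". The same sentence then gives the anchors: "where 0 represents no pain at all and 10 represents the highest pain the patient has ever felt". No other anchors are given for any diary item.

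Under Statistical Analysis (aim 1), the primary outcome is PLP on a VAS. The six covariates are baseline pain, limb level, etiology, laterality, age and gender. Models for secondary outcomes are described as exploratory, and those outcomes are not named.

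**The concern.** The diary paragraph attaches one pair of pain anchors to three items, one of which the protocol defines by the absence of pain. A subject who follows the anchors when rating sensation is grading pain. A subject who follows the item label instead is using a scale whose end points do not describe what is being rated. In neither case does the number have the meaning that the sensation definition gives it.

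What is at stake is the usability of the daily sensation record. Since the secondary outcomes are unnamed, an exploratory model of diary sensation is not ruled out. The study is also meant to supply data for designing a later randomized trial. A sensation series collected on pain anchors could not serve either purpose, because a change in it might reflect pain, sensation or the subject's way of coping with an ill-fitting scale.

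**Working it through.** The plan states no figure on this point, and no sample size, power or error-rate calculation enters it. The check is a comparison of the texts.

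**Step 1: item against anchors**

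| Item | Nature of the item | Anchors on its own VAS | Anchors in the diary paragraph | Compatible? |
|---|---|---|---|---|
| Strongest phantom limb episode | Pain intensity | Pain VAS: no pain to worst pain | No pain to highest pain ever | Yes |
| Stump pain | Pain | No pain to worst pain | No pain to highest pain ever | Yes |
| Phantom limb sensation | Non-painful by definition | No sensation to full sensation | No pain to highest pain ever | No |

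**Step 2: does the anchor clause cover sensation?** The diary sentence lists the items as "phantom limb sensation and stump pain on a colored visual analog scale included in the diary" and describes that single scale with a single pair of end points. It makes no exception for sensation. On the plain wording, the pain anchors apply to all three items.

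**Step 3: does the protocol otherwise match anchors to items?** Yes. Stump pain has pain anchors, phantom limb sensation has sensation anchors, and telescoping has a third set, from an enlarged phantom to one fully retracted. The diary paragraph is the exception.

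**Step 4: the logical limit.** Take a subject with a complete and entirely painless phantom. On the sensation VAS the score is 10. On the diary anchors, read literally, it is 0. The gap is 10 − 0 = 10 points, the full width of the scale. This shows that the two descriptions cannot both hold for one measure. It is a maximum and not an estimate of a typical discrepancy, because entry requires average pain of at least 4 out of 10 in the previous week and the documents do not show how subjects would answer.

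**Step 5: where the scores could enter the analysis.** Phantom limb sensation is neither the primary outcome nor one of the six covariates. The only possible route is the unnamed exploratory secondary models.

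**The case against.** The strongest reply is that the diary form is not in the documents. The protocol gives a short summary of it, two of the three items do suit pain anchors, and the sensation VAS is defined properly a few paragraphs above. The printed page may well carry the right anchors, with the summary loosely drafted. That stands: the text shows a wording error in the protocol but does not show that any collected score is wrong. It does not remove the point, because the protocol sentence is incorrect as a measurement rule whatever the form says.

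A second reply is that the diary serves monitoring and safety, and that no analysis of diary sensation is specified. That also stands and limits the severity. It does not exclude such an analysis, given the open-ended wording on secondary outcomes.

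A reader might infer several stronger things that the documents do not support:

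- **That the primary outcome is compromised**, because pain anchors on the sensation item blur the line between phantom pain and phantom sensation. Pain has its own pain-anchored VAS, the diary's strongest-episode item is also pain-anchored, and nothing shows how the sensation item would alter a PLP score.
- **That tDCS would falsely appear to reduce phantom sensation.** No planned analysis makes that claim, and the study is a single-arm, hypothesis-generating pilot.
- **That clinic and diary sensation scores would conflict.** The protocol does not say that the sensation VAS is a clinic-only instrument, and it plans no comparison or pooling of the two.
- **That about four weeks of sensation data per subject are affected.** Four weeks is the study length. The statement that recording runs to the end of the study is attached to the medication record, and no end date is given for the sensation item.

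**Conclusion.** The inconsistency is real on the face of the text and needs no outside source. As written, the diary rates a non-painful construct on pain anchors, and a score given that way would be uninterpretable as phantom limb sensation.

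The point is minor. It concerns one daily diary item. The primary model, the predictors, the sample size of 50 and the dedicated sensation VAS are not shown to be affected. Confidence is high in the mismatch of wording. No conclusion is available about the scores themselves: any practical effect assumes that the form in use reproduces the protocol's anchors and that subjects follow them, and neither can be determined from the documents.

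**What to change.** 1. In the diary paragraph, state anchors item by item. Give phantom limb sensation the protocol's own end points, "0- No phantom limb sensation, to 10 – Full sensation of the amputated limb", and label the item as non-painful. Keep pain anchors only for the strongest episode and stump pain.
2. Check the diary form against the corrected paragraph and reprint the page if it differs.
3. Only if the form in use carried pain anchors for sensation, analyse the sensation scores already collected on it separately from those collected on the corrected page. If the form was right all along, no data handling is needed.

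The cost is one protocol sentence and, at most, a reprinted diary page. The outcome definition, primary model and sample size stay as they are.
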